11.3.2.2 Best Overall Response (BOR)

BOR is defined as the best response per RECIST recorded from first dose of MM-398 until progression or start of new anti-cancer therapy and/or surgery. Designation of SD requires at least one assessment of stable disease at least 4 weeks after starting treatment. Patients with insufficient data for response classification will be classified as Not Evaluable for best overall response in the efficacy evaluable population.

The primary analysis for BOR will be based on the investigator-assessed response. BOR will be summarized by each cohort and overall for expansion phase. The analyses will be performed for efficacy evaluable population.

11.3.2.3 Objective Response Rate (ORR)

ORR is defined as the proportion of patients with a BOR characterized as either a Complete Response (CR) or Partial Response (PR) relative to the total number of evaluable patients, expressed as a percentage. Evaluable patients are the treated patients with measurable disease at baseline. Patients with insufficient data for response classification will be classified as non-responder for objective response in the efficacy evaluable population.

The primary analysis for ORR will be based on the investigator-assessed response. ORR will be summarized by each cohort and overall for expansion phase and exact 95% confidence intervals based on the binomial distribution will be reported. The analyses will be performed for efficacy evaluable population.

11.3.2.4 Clinical Benefit Response (CBR)

CBR₂₄ is defined as the proportion of patients with a BOR characterized as a Complete Response (CR) at any time, Partial Response (PR) at any time, or Stable Disease (SD) \geq 24 weeks relative to the total number of evaluable patients, expressed as a percentage. Evaluable patients are the treated patients with measurable disease at baseline.

The primary analysis for CBR will be based on the investigator-assessed response. CBR will be summarized by each cohort and overall for expansion phase and exact 95% confidence intervals based on the binomial distribution will be reported. The analyses will be performed for efficacy evaluable population.

11.3.2.5 Duration of Objective Response (DOR)

DOR is defined as the time from first documentation of response (CR or PR whichever occurs first, by investigator assessment) to the date of disease progression or to death due to any cause, whichever occurs first. Duration of response will be computed only for patients who have CR or PR as best overall response. If progression or death does not occur for a patient with response, the patient's duration of response will be censored in accordance with the rules used for PFS analysis. Duration of objective response will be calculated for all patients that experience documented objective response during the study in weeks as follows:

Duration of DOR (Months) = ((Date of Progression/Death/Censoring - Date of First Recorded CR or PR)+1) *12/365.25

The primary analysis for DOR will be based on the investigator-assessed response. DOR will be summarized by each cohort and overall for expansion phase. The analyses will be performed for efficacy evaluable population.

Imaging - Related:

Pilot Phase:

- **To estimate the correlations between FMX-MRI, TAM levels, and tumor levels of irinotecan and SN-38 with administration of MM-398**
Scatter plot of FMX-MRI vs. tumor SN-38 level, TAM level and irinotecan level will be presented. For FMX-MRI, corrected FMX results across all scanned lesions at the same timepoint for a patient will be used. If there is more than one image data at the same timepoint for a patient, image data will be averaged first before summarizing.
- **To determine the value of FMX-MRI in directing tissue biopsy**
The value of FMX-MRI in directing tissue biopsy will be evaluated by summarizing the feasibility of ferumoxytol (FMX) quantitation in tumor lesions, feasibility of FMX-MRI to identify tumor associated macrophages (TAM), and the relationship assessment between ferumoxytol (FMX) tumor uptake and tumor response.

Expansion Phase

- **To assess the association between deposition, as visualized by ferumoxytol imaging, and measures of efficacy**
The association will be performed on per lesion basis. The analysis will be combined into primary endpoint analysis "The Relationship Between Ferumoxytol (FMX) tumor uptake and tumor response to MM-398" in section 11.1
- **To assess the analytical performance of FMX-MRI measurements and optimize FMX-MRI parameterization**
The analytical performance of FMX-MRI measurements will be evaluated by summarizing phantom slopes and intercepts from all scans per instrument (site) and per instrument type (1.5 vs 3T). For each instrument or instrument type phantom slopes and

intercepts will be summarized per acquisition method (FSPGR vs MGRE) and per phantom type (body, head). The phantom slope over time will be summarized as rate of change (stability).

Heterogeneity of lesion signal on baseline scan and 24h scan repeats will be summarized (interscan lesion signal CV%; FSPGR and avg MGRE). Heterogeneity of signal between MGRE scan repeats will be summarized (intrascan lesion signal CV%).

Optimization of FMX-MRI parameterization will be evaluated by grouping FMX signals at 4 hour and 24 hours relative to the median value observed in the evaluable lesions and comparing these groups with the best change in lesion size seen by imaging (CT/MRI). Contrast to noise ratios of FMX lesion signals will be evaluated between responding and non-responding lesions (CR/PR) at all scan times.

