10.3 Statistical Analysis

Detailed methodology for summary and statistical analyses of the data collected in this study will be documented in a Statistical Analysis Plan (SAP), which will be dated and maintained by the Sponsor. The SAP may modify the analysis outlined in the protocol; however, any major modifications of the primary endpoint and/or its analysis will also be reflected in a protocol amendment.

No formal hypothesis testing will be performed in the Pilot or Expansion Phases of this study. Descriptive statistics will be calculated to summarize categorical and continuous parameters. Parameters will be reported by cohort and overall, according to Pilot and Expansion Phase. When appropriate, the Pilot and Expansion study phases may be pooled. At the minimum, categorical parameters will be summarized by frequency and percentage, while continuous parameters will be summarized by n, mean, standard deviation, median, minimum and maximum. Time-to-event parameters will be graphically displayed using Kaplan-Meier estimates. Median event times and 2-sided 95% confidence intervals will be reported on the graphs. Two-sided 95% confidence intervals (CI) may be displayed for some other parameters. All analyses will be performed in SASv9.2 or higher. No interim analysis will be performed.

A cycle is defined as 28 days in length starting with Cycle 1 Day 1 as the first dose date of MM-398. Data will be analyzed according to the cycle in which it actually occurred.

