11.3.2.1 Progression-Free Survival (PFS)

PFS is defined as the time in months from first dose of MM-398 to the date of radiologic disease progression by RECIST or mRECIST (cohort 3 CNS disease) per Investigator assessment or death due to any cause, whichever occurs first.

Date of Progression: the earliest date that an overall tumor response of PD or death is recorded. Data handling conventions for determining the date of progression are outlined in [Table 3](#).

If progression is associated with a new lesion, the date of progression is the date when the new lesion was detected, where progression is associated with the sum of target lesions and different lesions are measured on different dates in a given visit, use the earliest date for visit as the date of progression.

For patients who do not have qualifying progressive disease or death, the date of censoring for PFS is the date when the last valid tumor assessment determined a lack of progression. If the last valid tumor assessment involves measurements over multiple days in a visit, the date of the last measurement will be the censoring date. A tumor assessment is considered valid if data has been recorded for all target lesions and absence of new lesions is documented. Date of last non-PD/non-NE assessment is the date of first dose date for patients without a valid post-baseline tumor assessment.

Table 3 Data handling rules for PFS analysis

Condition	Date of Progression or Censoring	Event
No baseline tumor assessments	Date of first dose of MM-398	Censored
Progression documented within 12 weeks* of baseline or the last non-PD/non-NE tumor assessment	Earliest of: 
 • date of radiographic assessment showing new lesion (if progression based on new lesion) or • date of radiographic assessment of target/non-target lesions in which progression is documented 	Progression
Death within 12 weeks* of last non-PD tumor assessment without documented progression	Date of death	Progression
Death or first documented progression after 12 weeks* from last non-PD tumor assessment	Date of last non-PD assessment	Censored
None of the following: 
 • documented progression • death • treatment termination • New anticancer therapy started • cancer-related surgery 	Date of last non-PD assessment	Censored

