Treatment termination for clinical deterioration without documented progression or death	Date of last non-PD assessment or date of first dose of study drug MM-398 if no evaluable post-dose tumor assessment	Censored
Treatment termination for adverse event or other reason without documented progression or death	Date of last non-PD assessment or date of first dose of study drug MM-398 if no evaluable post-dose tumor assessment	Censored
New anticancer therapy started prior to treatment termination without documented progression	Date of last non-PD assessment prior to start of new anticancer therapy or date of first dose of study drug MM-398 if no evaluable post-dose tumor assessment	Censored
Cancer-related surgery prior to documented progression	Date of last non-PD assessment prior to cancer related surgery or date of first dose of study drug MM-398 if no evaluable post-dose tumor assessment	Censored

*16 weeks will be used for PFS sensitivity analysis

As a sensitivity analysis, PFS will also be analyzed following the same censoring rule in table 3 with 16 weeks of baseline or the last non-PD/non-NE tumor assessment time window being applied.

Progression-Free Survival (PFS) will be presented for each cohort and overall for expansion phase.

PFS assessed by investigator will be analysed using Kaplan-Meier method and descriptively summarized at 3 months interval for each dose level cohort. Median PFS time and corresponding 95% confidence limits will be presented.

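### Read literally, the SAP's duration-of-response rule can count a responder as an event after a date at which PFS has already censored that same patient

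*SAP*

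**What the plan says.** **DOR (SAP 11.3.2.5).** Time runs from the first CR or PR "to the date of disease progression or to death due to any cause, whichever occurs first. Duration of response will be computed only for patients" with CR or PR as best response. The PFS censoring rules are then brought in on one condition only: "If progression or death does not occur for a patient with response". The formula is "Duration of DOR (Months) = ((Date of Progression/Death/Censoring - Date of First Recorded CR or PR)+1) *12/365.25".

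**PFS (SAP 11.3.2.1 and Table 3).** The text censors patients who lack a *qualifying* progression or death. The DOR sentence has no such qualifier. Three rows of Table 3 matter here, and all three censor at an earlier non-PD assessment:

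- "Death or first documented progression after 12 weeks* from last non-PD tumor assessment"
- "Cancer-related surgery prior to documented progression"
- "New anticancer therapy started prior to treatment termination without documented progression"

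The 12-week limit becomes 16 weeks in the PFS sensitivity analysis.

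**Protocol 10.6** defines DOR with the same two end events and no censoring rule. It leaves only the PFS event and censoring rules to the SAP.

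**The concern.** The trigger for DOR censoring is that no progression or death occurs. The late-event and surgery rows of Table 3 concern patients in whom progression or death may well occur. For a responder in either row the DOR condition is false, so nothing in 11.3.2.5 brings Table 3 into play. DOR then ends in an event at the observed date, while PFS stops earlier and is censored.

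A response lies inside the patient's progression-free time, so a DOR longer than that patient's own PFS cannot be explained to a reader of the report. Two programmers could also derive different DOR data sets from the same text. The SAP's best-response rule (11.3.2.2) stops counting at new therapy or surgery, so a DOR that runs on past surgery departs from that rule as well as from PFS.

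**Working it through.** The documents give no DOR figure to reproduce. The check applies both rules, as written, to constructed patients.

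**Inputs**
- Scans every 8 weeks from the start of MM-398 (SAP 11.3.1), with a window of ±7 days (Protocol 8.2).
- Late-event limit: 12 weeks, or 84 days; 16 weeks, or 112 days, in the sensitivity analysis (Table 3).
- Months = (end − start + 1) × 12/365.25, that is, days divided by 30.4375 (SAP 7.6.4.1 and 11.3.2.5).
- First dose is day 1, so weeks 8, 16, 24 and 32 are days 57, 113, 169 and 225.

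**Condition for DOR to exceed PFS.** Let F be first dose, R first response, L the last non-PD assessment that Table 3 uses, and E the event. Literal DOR is E − R + 1 days and censored PFS is L − F + 1 days. DOR is therefore longer exactly when E − L > R − F, that is, when the gap before the event exceeds the time to response.

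**Patients, 12-week rule**

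| Patient | PFS under Table 3 | DOR as written | DOR if Table 3 applied |
|---|---|---|---|
| 1. PR wk 8, last non-PD wk 16, wk 24 missed, PD wk 32 | 113/30.4375 = 3.71, censored | 169/30.4375 = 5.55, event | 57/30.4375 = 1.87, censored |
| 2. PR and last non-PD wk 8, wk 16 missed, PD wk 24 | 57/30.4375 = 1.87, censored | 113/30.4375 = 3.71, event | 1/30.4375 = 0.03, censored |
| 3. PR wk 8, surgery wk 10, PD wk 24 | 1.87, censored | 3.71, event | 0.03, censored |
| 4. PR wk 8, non-PD wk 16, surgery wk 18, PD wk 24 | 3.71, censored | 3.71, event | 1.87, censored |
| 5. PR wk 8, non-PD wk 16, PD wk 24, nothing missed | 169/30.4375 = 5.55, event | 3.71, event | 3.71, event |

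Patients 1 to 3 have a DOR longer than their PFS. In patient 4 the times are equal and only the status conflicts. Patient 5 shows no conflict. One missed scan leaves a nominal 16-week gap, so it is enough to trigger the 12-week rule.

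**16-week window.** Patient 1's gap is exactly 16 weeks, so PFS becomes an event at 225/30.4375 = 7.39 months and the conflict disappears. With a 17-week gap (PD on day 232), PFS is still censored at 3.71 while DOR is an event at 176/30.4375 = 5.78. The surgery cases are unchanged.

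**Direction on the median.** Kaplan-Meier passes a censored responder's weight to those still in response, so the effect depends on the other responders. Two invented sets show both directions:
- *Up.* Patient 1 plus events at 1.87, 3.71, 7.39 and 9.23 months. As written, the median of the five is 5.55. With Table 3, survival is 4/5 = 0.80 at 1.87, then 0.80 × 2/3 = 0.53 at 3.71, then 0.53 × 1/2 = 0.27 at 7.39. The median is 7.39.
- *Down.* A responder like patient 1 who misses weeks 24 and 32 and has PD at week 40 (literal DOR 225/30.4375 = 7.39), plus events at 3.71 and 5.55. As written, the median is 5.55. With Table 3, survival reaches 1/2 at 3.71. The median is 3.71, or 4.63 if the midpoint of 3.71 and 5.55 is taken.

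**Weight of one patient.** At the SAP's hypothesised 30% ORR, 0.30 × 30 = 9 responders are expected, about 3 per cohort. If one such patient occurs, that is 1/9 = 11% of the overall DOR data and about a third of a cohort's.

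**The case against.** **A coherent reading is available.** SAP 11.3.2.1 defines the date of progression and points to Table 3 for it. The DOR formula reuses that term, and the DOR text sends censoring to the PFS rules. On this reading a late progression does not qualify for either endpoint. That is plausible and may be what was meant. But 11.3.2.5 does not say so, drops the qualifier used for PFS, and names death from any cause as a separate end event with no limit on timing.

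**Few patients can be affected.** Other anti-neoplastic therapy is not permitted on trial (Protocol 6.5). Scheduled follow-up ends with one visit 30 days after the last dose, and no survival follow-up is planned. Late deaths and progressions will seldom be recorded. This stands. What remains is mainly the responder who misses a scan while on treatment, or who has cancer surgery on study.

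**Counting an observed event is defensible.** It agrees with Protocol 10.6, and the correction turns observed events into earlier censored times. This also stands, as a cost of the fix and as a reason a sponsor might choose a different DOR rule on purpose. The SAP does not state such a choice.

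**A reader might infer more than the text supports.** One might say that new anticancer therapy creates the same conflict. That row is limited to patients without documented progression, so it is an ambiguous and weaker route. One might also say that DOR lacks a Kaplan-Meier analysis, but Protocol 10.3 already provides that "Time-to-event parameters will be graphically displayed using Kaplan-Meier estimates".

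**Conclusion.** The inconsistency is real on the wording of SAP 11.3.2.5, and the late-event and surgery rows of Table 3 are enough to establish it. It rests on reading the conditional sentence literally. If the sponsor always meant Table 3 to apply, the correction changes no result and only removes the ambiguity.

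Its size is small. The documents give no frequency for missed scans or surgery among responders, so the 11% and one-third figures hold only if such a patient occurs. A reader might infer that median DOR is inflated, or usually biased upward. The documents do not support this: the worked sets move in opposite directions. Nor does every affected patient have a DOR longer than PFS, since the gap must exceed the time to response. DOR is a secondary, descriptive endpoint in a trial without formal hypothesis testing. This is a minor correction.

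**What to change.** Replace the conditional censoring sentence in SAP 11.3.2.5 with: *For every responder, the DOR end date and event/censoring status are those of the PFS analysis (Table 3); time starts at first documented CR or PR.*

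This reuses existing PFS variables and ensures that DOR cannot exceed PFS. It gives no negative durations, because a response is itself a non-PD assessment and 11.3.2.2 counts only responses before new therapy or surgery. The price is that some observed late events become earlier censored times, as short as one day for patients 2 and 3. DOR will carry more censoring and its median may move either way. If the sponsor prefers to keep observed late events in DOR, the SAP should state that difference and the reason.

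A 16-week DOR sensitivity analysis is optional. While the section is open, its text should be reconciled with its formula: the text gives DOR in weeks and the formula in months.

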Tumor evaluation will be measured according to Response Evaluation Criteria In Solid Tumors (RECIST) version 1.1 for non-CNS disease, or according to modified RECIST criteria as defined in this protocol for CNS disease. Tumor evaluations will be characterized according to best overall response (BOR), duration of response (DOR), progression-free survival (PFS), and clinical benefit rate (CR, PR, or SD \geq 24 weeks). Objective response rate (ORR) and BOR will be summarized using frequency and percentage. PFS will be described using Kaplan-Meier methods.
FMX uptake will be summarized as a continuous parameter. Box and whisker plots will be displayed for FMX uptake. The relationship between FMX uptake and tumor response will be evaluated using various parameters and methods. Relationships may be explored as appropriate. Additionally, informal Fisher's exact test will be used to investigate dichotomous FMX cut-points as related to ORR. Other graphical procedures may be implemented to explore the relationship between FMX and efficacy response.
 Spearman pairwise correlations will be computed between the following measurements: FeMRI levels Tumor associated macrophage levels Tumor irinotecan levels Tumor SN-38 levels
Graphical and regression methods will be used to explore potential relationships among correlated measurements. In addition, relationships between

	pharmacodynamics markers and efficacy response will be evaluated in an exploratory manner.
	PK parameters will be derived from the blood PK samples and will be analyzed using descriptive statistics, including the median, mean and 95% confidence intervals around parameter estimates by dose level. All PK parameters will include Cmax, Tmax, AUC (area under the concentration curve), clearance, volume of distribution at steady state (Vdss), and the terminal elimination half-life. Estimation of the pharmacokinetic parameters will be performed using standard non-compartmental methods.
Sample Size Justification	No formal hypothesis testing will be performed for this study. The Pilot Phase will enroll 12-20 patients in a variety of indications, while the Expansion Phase will enroll approximately 30 patients with metastatic breast cancer within 3 cohorts. Although no formal sample size calculation was performed for either study phase, the anticipated response rate in the HER2 negative Expansion Phase is estimated around 29% [36].

2 Background Information and Rationale

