10.9 Pharmacodynamic Marker Analysis

Spearman pairwise correlations will be computed between the following measurements obtained from the Pilot Phase of the study:

- FMX-MRI levels
- Tumor associated macrophage levels
- Tumor irinotecan levels
- Tumor SN-38 levels

Graphical and regression methods will be used to explore potential relationships among correlated measurements. In addition, relationships between pharmacodynamics markers and efficacy response will be evaluated in an exploratory manner in both the Pilot Phase and Expansion phases of the study.

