2.2 Secondary Objectives

All Phases:

- To characterize the safety profile of MM-398 in the presence of FMX
- To assess tumor response to treatment
- To characterize the pharmacokinetics (PK) of MM-398

Pilot Phase (Completed):

- To estimate the correlations between FMX-MRI, TAM levels, and tumor levels of irinotecan and SN-38 with administration of MM-398
- To determine the value of FMX-MRI in directing tissue biopsy

Expansion Phase:

- To characterize the efficacy of MM-398 in patients with locally advanced or metastatic breast cancer using key efficacy indicators such as objective response rate and clinical benefit rate
- To assess the association between deposition, as visualized by ferumoxytol imaging, and measures of efficacy
- To further characterize the safety profile of MM-398, in the presence of FMX, in patients with metastatic breast cancer
- To assess the analytical performance of FMX-MRI measurements and optimize FMX-MRI parameterization

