3 STUDY DESIGN

3.1 General Design and Plan

This study comprises two phases: pilot phase and expansion phase.

Pilot phase will enroll approximately 12 patients, up to 20 in total. The first three patients that are enrolled can have any solid tumor type; however subsequent patients must have NSCLC, CRC, TNBC, ER/PR positive breast cancer, pancreatic cancer, ovarian cancer, gastric cancer, gastro-oesophageal junction adenocarcinoma or head and neck cancer. No more than three patients with ER/PR positive breast cancer can be enrolled in the Pilot Phase and similar restrictions may be placed on other tumor types to ensure a heterogeneous population.

These indications were selected based on data suggesting that these tumor types have high levels of CD68 (tumor associated macrophages) and carboxylesterase enzyme (CES) activity or high levels of deposition, any of which may correlate to MM-398 response.

The Expansion Phase will enroll cohorts of single indications of patients with locally advanced or metastatic breast cancer in 3 cohorts of 10 patients each depending on sub-type of breast cancer:

- Cohort 1: ER and/or PR-positive breast cancer
- Cohort 2: Triple negative breast cancer (TNBC)
- Cohort 3: Breast Cancer (BC) with active brain metastasis

There are four stages to each phase of this study:

- Screening (-28d): patients undergo screening assessments to determine if they are eligible for the study
- Ferumoxytol (FMX) (Day 1 Day 2): patients receive ferumoxytol infusion and undergo required FMX-MRI scans and pre-treatment biopsy (if applicable, see Cohort requirements) prior to receiving MM-398
- MM-398 Treatment (C1D1 progression of disease): patients receive an MM-398 dose of 60 mg/m² every 2 weeks, which should be dose escalated to 80 mg/m² every 2 weeks in subsequent doses depending on patient tolerance, other required assessments, and undergo a post-treatment (MM-398) multiple pass core biopsy
- Follow up (+30d from last dose): patients return to clinic 30 days after their last dose of MM-398 for final safety assessments

Ferumoxytol magnetic resonance imaging (FMX-MRI) will be done for both pilot phase and expansion phase. The schedule for pilot phase FMX-MRI is: pre-dose of ferumoxytol, 1-4 hours post dose and 24 hours post dose of ferumoxytol.

The schedule for expansion phase is outlined in Tables 1 and 2:

Table 1 Summary of Expansion Phase MRI Scan Groups (Cohorts 1 and 2)

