11 EFFICACY ANALYSES

11.1 Primary Efficacy Endpoints:

The efficacy endpoints will be summarized for efficacy evaluable population and PD evaluable population by using descriptive statistics.

Pilot Phase:

- **Feasibility of FMX-MRI on identifying tumor associated macrophages (TAMs):**

FMX-MRI will be conducted on day 1 before and 1-4 h after intravenous ferumoxytol (FMX) administration, then after 24 h and/or 72 h. For the quality scan of FMX-MRI, scanner type (i.e. 1.5T), impact of scan quality on analysis (i.e. adequate for evaluation, suboptimal but completed for evaluation, or inadequate for evaluation), reasons for scan suboptimal/inadequate) and scan location (i.e. Body) will be assessed.

- **Tumor Levels of Irinotecan and SN-38:**

During pilot phase, two biopsies are collected on Day 4 of the ferumoxytol phase and two biopsies are collected three days after the first dose of MM-398. Tumor levels of irinotecan and SN-38 in core biopsy will be measured after MM-398 dosing.

Expansion Phase:

- **Feasibility of Ferumoxytol (FMX) Quantitation in Tumor Lesion**

Feasibility of ferumoxytol (FMX) quantitation in tumor lesion is also assessed through the acquisition of baseline and follow-up images of sufficient quality that enable quantitative analysis to be performed.

Eligible patients should have serial FMX-MRI scans prior to and following FMX infusion as determined by their scan group. After MRI acquisition, the R2* signal is used to calculate FMX levels in plasma, tumor lesions and reference tissue by comparison to a phantom-based standard curve.

- **The Relationship Between Ferumoxytol (FMX) tumor uptake and tumor response to MM-398**

FMX-MRI will be done for various tissues and at different timepoints. Corrected FMX uptake (post-baseline value - baseline value) will be recorded by each time point and tissues. Ferumoxytol uptakes will be associated with change in tumor lesion size.

11.2 Primary Efficacy Analysis:

Pilot Phase

In patients with NSCLC, CRC, TNBC, ER/PR positive breast cancer, pancreatic cancer, ovarian cancer, gastric cancer, GEJ adenocarcinoma or head and neck cancer, who are undergoing therapy with MM-398:

- To evaluate the feasibility of delayed ferumoxytol MRI (FMX-MRI) to identify tumor associated macrophages (TAMs)

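### The SAP plans no estimate for two Pilot secondary objectives: the protocol's Spearman correlations are reduced to three scatter plots, and the value of FMX-directed biopsy is judged without any tissue result

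*SAP*

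**What the plan says.** SAP 2.2 and protocol 3.2 both list two Pilot secondary objectives on imaging. One is to estimate the correlations between FMX-MRI, TAM levels and tumor irinotecan and SN-38. The other is "To determine the value of FMX-MRI in directing tissue biopsy".

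**Correlations.** Protocol 10.9 states: "Spearman pairwise correlations will be computed between the following measurements obtained from the Pilot Phase of the study". It lists FMX-MRI, TAM, irinotecan and SN-38, and adds graphical and regression methods for exploration. The synopsis makes the same Spearman commitment. The SAP's analysis is in the unnumbered Imaging-Related block that follows the duration-of-response text in 11.3.2.5: "Scatter plot of FMX-MRI vs. tumor SN-38 level, TAM level and irinotecan level will be presented". On the imaging input it says "For FMX-MRI, corrected FMX results across all scanned lesions at the same timepoint for a patient will be used", and several images at one time point are averaged. It does not say which time point is to be plotted.

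**Biopsy direction.** The same block says "The value of FMX-MRI in directing tissue biopsy will be evaluated by summarizing the feasibility of ferumoxytol (FMX) quantitation in tumor lesions". It adds two further inputs: feasibility of identifying TAMs, and the relationship of FMX uptake to tumor response.

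**The concern.** A scatter plot is not an estimate, so an objective worded as estimating correlations is left without one. The SAP names no correlation coefficient anywhere and gives no reason for dropping the protocol's. The question is central to the Pilot: protocol sections 2 and 2.2.3 justify the study by relating the imaging signal to MM-398 accumulation and activation.

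The biopsy objective has a stated method, but that method cannot answer it. Its output would be the same whether or not the core from the high-signal region differed from the core from the low-signal region.

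At stake is whether the study report can answer two objectives the SAP still lists. A lesser risk is that the FMX value plotted depends on an unstated choice of scan time point.

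**Working it through.** The plan gives no numerical figure for these analyses, so there is none to reproduce. The check compares the texts and then asks how precise the missing estimates could be.

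**1. Pairs.** Four measures give C(4,2) = 6 pairs under protocol 10.9. The SAP plots FMX against SN-38, TAM and irinotecan, which is 3 pairs with 0 coefficients and 0 intervals. TAM-irinotecan, TAM-SN-38 and irinotecan-SN-38 do not appear.

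**2. FMX time point.** SAP 3.1 says "The schedule for pilot phase FMX-MRI is: pre-dose of ferumoxytol, 1-4 hours post dose and 24 hours post dose of ferumoxytol", while SAP 11.1 says "FMX-MRI will be conducted on day 1 before and 1-4 h after intravenous ferumoxytol (FMX) administration, then after 24 h and/or 72 h". The correlation text chooses none of these. The Expansion analysis in SAP 11.2 does name the 24-hour scan.

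**3. Inputs to the biopsy objective.**

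| Input | How SAP 11.1-11.2 define it | Tissue result used? |
|---|---|---|
| Feasibility of FMX quantitation | Image adequacy (defined under Expansion) | No |
| Feasibility of identifying TAMs | Scan quality, scans obtained and accepted, scan location | No |
| Uptake versus response | Median-split FMX against change in lesion size, Fisher's exact test (defined under Expansion) | No |

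So 0 of 3 use tissue, even if the Expansion definitions are carried over to Pilot data. Protocol 7.3.1.1, by contrast, takes one core from the region of greatest signal change and one from the region of least, both before MM-398 and three days after the first dose.

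**4. Does other text fill the gap?** SAP 11.2 cites a synopsis report of 18 December 2014 and closes off further analysis, but only for irinotecan and SN-38 levels in the cores. SAP 13.1 only permits optional post-hoc biomarker work.

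**5. Precision if restored.** The numbers of assayed patients are not given. I take n=12 and n=20 (the planned Pilot range) and n=13 (the Pilot PK count in protocol 2.1.6). The rho values are assumptions.

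For Spearman's rho, the 95% interval is tanh[atanh(r) ± 1.96 × √((1 + r²/2)/(n − 3))]. With r = 0.5 and n = 13:
- atanh(0.5) = 0.549 and SE = √(1.125/10) = 0.335
- limits on the z scale are 0.549 ± 0.657, that is -0.108 and 1.207
- back-transformed, -0.11 to 0.84

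For a mean paired core difference, the 95% half-width in SDs of the differences is t(0.975, n−1)/√n. At n = 13 this is 2.179/3.606 = 0.60.

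| n | rho = 0.5 | rho = 0.7 | Paired half-width (SD) |
|---|---|---|---|
| 12 | -0.14 to 0.85 | 0.14 to 0.92 | 0.64 |
| 13 | -0.11 to 0.84 | 0.17 to 0.92 | 0.60 |
| 20 | 0.05 to 0.78 | 0.32 to 0.88 | 0.47 |

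A simulation with one bivariate-normal value per patient and a true Spearman of 0.5 gave Fisher-z coverage of 95.8%, 95.6% and 95.4% at n = 12, 13 and 20. The percentile bootstrap gave 96.2%, 95.7% and 95.2%. Either interval method would serve.

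**The case against.** The strongest reply has five parts.

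- **The SAP may change this.** Protocol 10.3 lets the SAP modify planned analyses and asks for an amendment only for major changes to the primary endpoint or its analysis. That stands, so there is no procedural breach. The inconsistency is inside the SAP, which keeps an estimation objective and plans no estimate.
- **The graphics are in the protocol too.** Protocol 10.9 also promises graphical methods, and the scatter plots deliver that part for three pairs. This is fair: what was lost is the coefficients for all six pairs and any display of the other three.
- **The core contrast is not in the protocol.** Correct. The biopsy half is a mismatch between objective and method, not a departure of the SAP from the protocol, and the contrast proposed below is a recommendation.
- **The results may already exist.** The Pilot is complete and the 2014 report is not available here. Whether it holds these results cannot be told from the documents. That limits what can be said about the consequence, but not the finding that this SAP neither plans nor cites the results.
- **Small n and unclear pairing.** The n=13 is a PK count, not a count of assayed biopsies. Post-dose cores come from a lesion not biopsied before, and the documents do not say which cores were assayed for TAM, so some TAM-drug pairs may cross lesions. These limits are real. They argue for printing an interval beside each plot and stating the pairing, not for leaving the estimate out.

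The time-point criticism is secondary. The text can be read as handling each time point separately, and figure shells may settle it.

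**Conclusion.** The concern holds. Followed as written, the SAP gives 3 plots and 0 estimates for 6 protocol-specified correlations, and judges biopsy direction on 3 inputs of which none uses tissue. These counts come straight from the documents and need no assumption.

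The precision figures do rest on assumptions about n and rho. On those, a rho of 0.5 would not exclude zero at n = 12 or 13, while a rho of 0.7 would at all three sizes. The results can only be descriptive, which fits a study without formal testing. The matter should be corrected because the two objectives are still listed, but they are secondary objectives in a descriptive Phase 1 study.

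**What to change.** 1. **Correlations.** Report the protocol 10.9 Spearman coefficients for all six pairs beside the plots, with 95% confidence intervals as an addition. Name the FMX scan time point and reconcile the Pilot schedules in SAP 3.1 and 11.1. State the tissue unit. Match FMX to the biopsied lesion where that value is stored. Correlate TAM with drug level within the same lesion where both were assayed there, otherwise at patient level.
2. **Biopsy direction.** As a descriptive addition without a test, report within-patient greatest-minus-least core differences with 95% confidence intervals: in TAM, and for post-dose cores in irinotecan and SN-38, wherever both cores were assayed.
3. **Alternative.** If the 18 December 2014 report already contains these results, cite it under the two objectives instead.

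The cost is SAP wording and modest programming on data the Pilot was designed to collect, with no new procedures; under option 3 it is only a citation. The drawbacks are wide intervals, the chance that region-level or lesion-level FMX values were not stored, and patients without two assayed cores.
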